6.1.5.1 Treatment beyond disease progression

Not applicable.

6.1.5.2 Tapering Guidelines

Tapering of corticosteroids, CNI, and ruxolitinib will follow 2 steps: first taper systemic corticosteroids following documented CR or PR, and follow with taper of CNI/ruxolitinib.

The taper of corticosteroids, in responding subjects (CR or PR) as outlined in [Table 6-2](#), must not be attempted earlier than approximately 2 weeks from the time of documented CR or PR. In responding subjects, the taper of ruxolitinib must not be attempted until the subject is off corticosteroids and CNIs AND the subject has completed the assessments for Cycle 7 Day 1.

During the Treatment Period, immunosuppression taper guidelines are:

- **Corticosteroids:** Every effort should be made to use the minimum dose of corticosteroid that is sufficient to control cGvHD manifestation. It is recommended that a taper of corticosteroids should be attempted approximately two weeks after achieving a documented CR or PR. Guidelines are included in [Table 6-2](#). If a flare should occur during the taper, the treatment should continue for at least 3 months prior to attempting to resume the taper.

Table 6-2 Corticosteroid taper guidelines

Week (time from achieving a CR or PR)	Dose, mg/kg body weight
0	Current dose of corticosteroid every (Q) day (example 1 mg)
2	Current dose of corticosteroid (1 mg)/ decrease alternate day dose by 50%* (0.5 mg)
4	Current dose of corticosteroid (1 mg)/decrease alternate day dose by 50%* (0.25 mg)
6	Current dose of corticosteroid every other day (QOD): 1 mg every other day
8	Decrease current dose of corticosteroid by 10% every 2 weeks until off

*Alternate-day administration
([Flowers and Martin, 2015](#))

- **CNI (cyclosporine or tacrolimus):** Once off systemic corticosteroids, and documented CR or PR, starting at Cycle 7 Day 1 at 25% dose reduction per month is allowed, or to be tapered per institutional practice.

- **Ruxolitinib:** Once off systemic corticosteroids, ruxolitinib taper is allowed in subjects demonstrating a CR or PR, starting no earlier than Cycle 7 Day 1. The following guidance may be followed based on evaluation of patient condition, current dosing regimen and the clinical judgement of Investigator: a 50% dose reduction every 2 months (approximately 56 days) can be initiated. If sustained cGvHD response is observed (i.e. no worsening of cGvHD signs and symptoms), subject can be further tapered by a second 50% dosage reduction based on investigator assessment and judgement.

6.1.5.2.1 cGvHD Flare

If a cGvHD flare occurs during the taper of any immunosuppressive medications, the dose of corticosteroids may be re-escalated at the Investigator's discretion and will not be considered treatment failure. If cGvHD flare requires initiation of a new systemic therapy due to inability to taper corticosteroids below methylprednisolone 1 mg/kg/day (or equivalent <1.25 mg/kg/day of prednisone) for a minimum 7 days, OR due to re-escalation of corticosteroids to methylprednisolone >2 mg/kg/day (or equivalent >2.5 mg/kg/day of prednisone), the subject will be considered to have experienced treatment failure.

If cGvHD flare occurs during ruxolitinib taper after Cycle 7 Day 1, subjects may have their ruxolitinib dose increased to the prior dose level, their response monitored, and ruxolitinib taper attempted again if subjects have a response within 28 days. If the flare is unresponsive to increased ruxolitinib dose within 28 days, or more than one flare is observed, the subject will be considered to have experienced cGvHD flare-failure, and further treatment with ruxolitinib is allowed per Investigator's judgement.

For any subject who develops severe worsening cytopenias necessitating abrupt interruption of ruxolitinib, flare of cGvHD may occur. To avoid significant cGvHD flare during abrupt ruxolitinib interruption, the subject's corticosteroid dose should be maintained or increased to ≥ 0.4 mg/kg/day methylprednisolone (or equivalent prednisone to ≥ 0.5 mg/kg/day) for a minimum 7 days after abrupt cessation of ruxolitinib. See [Section 6.5.1.1](#) for more details.

6.2 Other treatment(s)

6.2.1 Concomitant Medications

All medications, procedures and significant non-drug therapies (including physical therapy and blood transfusions) administered after the subject was enrolled into the study must be recorded on the appropriate eCRF.

Each concomitant drug must be individually assessed against all exclusion criteria/prohibited medication. If in doubt the investigator should contact the Novartis medical monitor before enrolling a subject or allowing a new medication to be started. If the subject is already enrolled, contact Novartis to determine if the subject should continue participation in the study.

Supportive treatments per institutional guidelines for management of alloSCT subjects with cGvHD or SR-cGvHD are allowed. The subject must be told to notify the investigational site about any new medications he/she takes after the start of treatment.

All medications (other than ruxolitinib and systemic corticosteroids) including over-the-counter medications and vitamins must be listed on the Concomitant Medications electronic case report

form (eCRF). Refer to [Section 6.2.2](#) for a list of prohibited concomitant medications during study treatment. Significant non-drug therapies (including physical therapy and blood transfusions) administered during the study must be listed on the significant non-drug therapies eCRF. Steroid usage in the 18 months prior to the first dose of ruxolitinib and any other prior medication received up to 30 days prior to the first dose of ruxolitinib must be recorded on the appropriate eCRF. Subjects will be instructed not to take any additional medications (including over-the-counter products) during the course of the study without consultation with the Investigator.

In addition to assigned ruxolitinib, subjects may receive standard alloSCT supportive care including anti-infective medications and transfusion support.

Use of CNIs (cyclosporine or tacrolimus) if initiated at least 3 weeks prior to the start of ruxolitinib (Cycle 1 Day 1), and topical corticosteroid therapy per institutional guidelines is permitted and must be listed on the corresponding concomitant medications eCRF.

Permitted concomitant medications are described in [Section 6.2.1.1](#).

On the days of the PK blood collection, subjects should be instructed to refrain from taking corticosteroids until after the last PK samples are collected (i.e., approximately 6 hours post-dose on Cycle 1 Day 1 and after the pre-dose sample collection on all other PK collection days). See [Section 8](#) for additional information.

Doses of methylprednisolone will be converted to prednisone equivalents by multiplying the methylprednisolone dose by 1.25. Prednisone doses for each subject are converted to mg/kg/day. For subjects that weigh over 100 kg, maximal starting dose of prednisone will be 200 mg (or 2 mg/kg/day based on a modified starting weight of 100 kg). For calculation of subsequent prednisone doses/kg on subsequent measures, the modified starting weight of 100kg will be used.

6.2.1.1 Permitted concomitant medications requiring caution and/or action

Subjects receiving ruxolitinib with concomitant medications provided per standard institutional guidelines for management after alloSCT including: anti-emetics, CNIs, azole fungal prophylaxis, broad spectrum antibiotics in the event of fever (either semi-synthetic penicillin or third generation cephalosporin with vancomycin, gentamicin or equivalent), acyclovir prophylaxis, ganciclovir, foscarnate, granulocyte colony stimulating factor (G-CSF), steroid pre-medications prior to RBC/platelet transfusions, narcotics, and sedatives warrant close monitoring of potential drug-drug interaction effects of these concurrent drugs.

Ruxolitinib dose adjustments may be required, particularly in subjects treated with CYP450 modulators (See [Section 6.5.1.3](#)).

Upon initiation of a strong CYP3A4 inhibitor or a dual CYP3A4/CYP2C9 inhibitor, including fluconazole up to a dose of 6 mg/kg (maximum 200mg) daily, the dose of ruxolitinib should be considered to be reduced (e.g. by 50%), and more frequent monitoring of hematology parameters and clinical signs and symptoms of ruxolitinib related adverse events is recommended. The subject and the Investigator should be aware of potential signs of overdose of the concomitant medications and in the event of suspected study drug related toxicity, administration of ruxolitinib should be dose reduced or held according to guidelines (See

[Table 6-4](#)) and Investigator judgment, with appropriate corticosteroid immunosuppression provided to avoid cGvHD flare.

6.2.2 Prohibited medication

The following therapies are prohibited during the study until ruxolitinib treatment discontinuation:

- Due to the high risk of bleeding in alloSCT subjects with cGvHD or SR-cGvHD, systemic Nonsteroidal anti-inflammatory drugs (NSAIDs) and related medications that would expectedly reduce platelet function, and/or heparin, Vitamin K antagonists (e.g., warfarin), aspirin and other oral anticoagulants or related medications that would adversely affect blood coagulation are prohibited. **Note:** Heparin or Low Molecular Weight Heparin (LMWH) is allowed if used at sub-therapeutic dose for e.g., prophylaxis of sinusoidal obstructive syndrome/veno-occlusive disease of the liver.
- Concomitant use of another JAK inhibitor besides ruxolitinib.
- Any investigational medication (other than ruxolitinib) that is not approved for any indication. Use of such medications is prohibited within 30 days or 5 half-lives, whichever is longer, prior to the first dose of ruxolitinib and until treatment discontinuation.
- Use of chemotherapeutic agents and/or non-scheduled DLI for malignancy recurrence/relapse is not permitted. If required for subject management, the subject is discontinued from study treatment.
- Any pre-emergent intervention related to graft failure or underlying disease relapse/recurrence including but not limited to: stem cell graft boost, additional conditioning chemotherapy or anti-T-cell therapy, non-scheduled DLI, and/or abrupt cessation/taper immunosuppression is not permitted. If required for subject management, the subject is discontinued from study treatment
- Administration of fluconazole at daily doses higher than 6 mg/kg (maximum 200 mg) ([Section 6.2.1.1](#))
- Addition of any new systemic immunosuppressive therapy after start of ruxolitinib may be decided by the Investigator. In this case, the subject must discontinue ruxolitinib ([Section 9.1.1](#)). Rituximab can be administered for the treatment of EBV. EBV infection must be captured either in the Medical History or Adverse Event eCRF.
- Herbal preparations/medications are not allowed, as a potential drug-drug interaction is possible. These herbal medications include, but are not limited to, St. John's Wort, Kava, ephedra (ma huang), gingko biloba, dehydroepiandrosterone (DHEA), yohimbe, saw palmetto, and ginseng. Subjects must stop using herbal medications at least 7 days prior to first dose of study treatment.
- Considering the underlying population with immunocompromised state and ruxolitinib therapy, use of live-attenuated vaccines (i.e., against SARS-CoV-2) are prohibited. The restriction of vaccines is applicable during study treatment. [Note: the use of mRNA SARS-CoV-2 vaccines are permitted.]

6.2.3 Rescue medication

Not applicable.

6.3 Subject numbering, treatment assignment, randomization

6.3.1 Subject numbering

Each subject is identified in the study by a Subject Number (Subject No.), that is assigned when the subject is first enrolled for screening and is retained as the primary identifier for the subject throughout his/her entire participation in the trial. The Subject No. consists of the Center Number (Center No.) (as assigned by Novartis to the investigative site) with a sequential subject number suffixed to it, so that each subject is numbered uniquely across the entire database. Upon signing the informed consent form (ICF) and assent form, if appropriate, the subject is assigned to the next sequential Subject No. available.

The investigator or designated staff will contact the Interactive Response Technology (IRT) and provide the requested identifying information for the subject to register them into the IRT. Once assigned, the Subject No. must not be reused for any other subject. If the subject fails to start treatment for any reason, the reason will be entered into the appropriate Disposition page.

IRT must be notified within 2 days that the subject will not be entering the treatment phase of the study.

6.3.2 Treatment assignment, randomization

This is a non-randomized study. The assignment of a subject to the appropriate dosing group will be based on age using the IRT system and coordinated by Novartis.

6.4 Treatment blinding

Treatment will be open to subjects, parent/legal guardians, caregivers, investigator staff, persons performing the assessments, and the Novartis Clinical Trial Team (CTT).

6.5 Dose escalation and dose modification

A standardized dosing paradigm will be used to determine dose adjustments for safety and efficacy so that each subject is titrated to their most appropriate dose. These changes must be recorded on the Dosage Administration Record eCRF.

6.5.1 Dose modifications

For subjects who do not tolerate the protocol-specified dosing schedule, dose interruptions and/or reductions are either recommended or mandated in order to allow subjects to continue ruxolitinib.

These dose modifications are summarized in [Table 6-3](#). Deviations to mandatory dose interruptions and/or reductions are not allowed. Permanent treatment discontinuation is mandatory for specific events indicated as such in [Table 6-3](#).

Based on the subject's age, the ruxolitinib dose will not exceed the starting dose level defined for that age Group. The dose for CNI and/or corticosteroids can be modified as per Investigator discretion, institutional guidelines, or as per product label.

A standardized dosing paradigm in [Table 6-4](#) and [Table 6-5](#) will be used to determine dose adjustments for safety and efficacy so that each subject is titrated to their most appropriate dose. These dose changes must be recorded on the Dosage Administration Record eCRF.

A more frequent schedule of safety assessments is recommended (i.e. every 2 weeks) after restarting ruxolitinib due to a dose hold.

If a subject requires a dose interruption of > 21 days from ruxolitinib, then the subject must be permanently discontinued from ruxolitinib, and will be entered into early discontinuation follow-up with assessments as described in [Table 8-1](#).

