This open-label, single-arm, Phase II multi-center study will investigate the activity, pharmacokinetics and safety of ruxolitinib added to the subject's immunosuppressive regimen among infants, children, and adolescents aged ≥ 28 days to < 18 years old with either moderate to severe treatment-naïve cGvHD or SR-cGvHD. Approximately 42 subjects will be enrolled in this study. Subjects will be grouped according to their age as follows: Group 1 includes subjects ≥ 12 y to < 18 y, Group 2 includes subjects ≥ 6 y to < 12 y, Group 3 includes subjects ≥ 2 y to < 6 y, and Group 4 includes subjects ≥ 28 days to < 2 y. Subjects will remain in the age group throughout the study based on the age at the time of start of treatment. Enrollment initiation into the youngest age group, Group 4, will be subject to the availability of data in this age group from study [CINC424F12201], as well as a review of available PK, safety, and activity data generated from Groups 1 to 3 in the current study, in consultation with the data monitoring committee (DMC) and a final decision by the Sponsor. At least 5 evaluable subjects per Group are needed for the primary analysis in Groups 1, 2 and 3. No minimum number of evaluable subjects are needed in Group 4.

[figure not shown]
After a screening period from Day -28 to Day -1, eligible subjects will begin the investigational treatment (ruxolitinib) on Cycle 1 Day 1 and will be treated for up to a maximum of 3 years (39 cycles/ 156 weeks) or until early discontinuation. Subjects who discontinue ruxolitinib for any reason earlier than 39 cycles will be followed every 6 months until 3 years from their first dose of ruxolitinib is reached. Refer to [Section 8.2.1](#) for details of the treatment period study visits. All subjects continuing to receive ruxolitinib treatment benefit following 3 years of treatment will be given the possibility to continue ruxolitinib outside the study, from another source, where permitted in accordance to local laws and regulations.

The ruxolitinib dose is based on the preliminary efficacy and safety data generated with this dose in subjects with steroid-refractory graft vs. host disease (SR-GvHD) ([Zeiser et al 2015](#)), and based on PK/safety data generated from the Phase III trials CINC424C2301 and CINC424D2301. As subjects ≥ 12 y to < 18 y are already being treated with 10 mg BID in CINC424D2301, this dose is the recommended phase II dose (RP2D), and will be used to treat all subjects in this age group.

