4.2 Rationale for dose/regimen and duration of treatment

Pharmacokinetic predictions in pediatrics with GvHD were based on PK in adults with GvHD (clinical study CINC424C2301). Two methods were used to derive an efficacious and safe dose of ruxolitinib in pediatric population for the Graft vs. Host Disease indication:

1) allometric scaling method in which the exponents used for scaling were obtained as described by (Mahmood 2014);

and

2) Physiologically based pharmacokinetic (PBPK) modeling using the SimCYP software in which the already established and validated model that matched the PK profiles in healthy adults (5-25 mg BID) was adapted to match the PK profiles obtained in adults with GvHD (10 mg BID; clinical study CINC424C2301). Then changing the body physiology from adults to a pediatric population (available in SimCYP) enabled the prediction of ruxolitinib clearance and drug exposure in pediatrics. The assumption that efficacy is driven by drug exposure is supported by a study in children with solid and hematological malignancies (Loh et al 2015).

Overall, for an age above 2 years old the predicted doses were very similar by using either allometry or PBPK scaling, therefore the starting doses in pediatric patients were assessed by averaging the predictions from both approaches. For an age below 2 years old, the predictions from PBPK model that incorporate ontogeny (un-mature polymorphic cytochrome P450 enzymes (CYPs) in pediatrics) predicted a lower CL and doses than allometry and thus a conservative approach will be used for this group.

The predicted efficacious doses in children that would match the drug exposure observed in adult with a dose of 10 mg BID (e.g. AUC0-12h: 539 ng.h/mL equivalent to 1750 h.nM (Shi et al 2011, Shi et al 2012) were: 1.4 to 2.7 mg/m² BID for the youngest patients (\geq 28 days to < 2 years); 4 mg/m² BID for 2-6 years; 5 mg BID for 6-12 years; and 10 mg BID for 12-18 years.

The PBPK model predictions for the lower age-groups (\geq 28 days to < 2 years) will be readjusted when PK information in the higher age groups (between 2 and 18 year old) will become available.

Ruxolitinib will be administered either as a 5 mg tablet or as an oral pediatric formulation twice a day, added to standard treatment of cGvHD including methylprednisolone +/- CNI at standard dosing adjusted to therapeutic trough levels.

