6.1.1 Investigational and control drugs

Table 6-1 Dose and treatment schedule

Investigational treatment	Age groups	Pharmaceutical form and Route of Administration	Dose	Frequency and/or Regimen
Ruxolitinib (INC424)	Group 1 ≥ 12 years old to < 18 years old	5 mg tablet* for oral use OR oral pediatric formulation	10 mg BID (2 tablets orally BID) OR 10 mg BID oral pediatric formulation**	Twice per day
Ruxolitinib (INC424)	Group 2 ≥ 6 years old to < 12 years old	5 mg tablet* for oral use OR oral pediatric formulation*	5 mg BID (1 tablet orally BID) OR 5 mg BID oral pediatric formulation**	Twice per day

Investigational treatment	Age groups	Pharmaceutical form and Route of Administration	Dose	Frequency and/or Regimen
Ruxolitinib (INC424)	Group 3 ≥ 2 years old to < 6 years old	5 mg tablet* for oral use OR oral pediatric formulation	4 mg/m ² BID (either tablet orally OR oral pediatric formulation)**	Twice per day
Ruxolitinib (INC424)	Group 4 ≥ 28 days to < 2 years old	oral pediatric formulation	X mg/m ² BID (oral pediatric formulation)** To be defined from study CINC424F12201	Twice per day

*A whole tablet for oral use may be crushed as per instructions in the pharmacy manual (if calculated dose based on BSA is not 5 mg or 10 mg, then crushing is not permitted. Tablet cannot be broken to achieve partial doses. In this case, oral pediatric formulation should be administered). Oral pediatric formulation should be dispensed according to instructions in the pharmacy manual.
Note: Crushed tablet(s) can only be administered orally and cannot be administered by nasogastric (NG) tube.
**Calculated doses should be rounded to the nearest available volume as per instructions in the pharmacy manual

The Investigator will instruct the subject to take the investigational treatment as per protocol.

All dosages prescribed and dispensed to the subject and all dose changes during the study must be recorded on the Dosage Administration Record electronic case report form (CRF).

Ruxolitinib will be administered orally twice per day at the assigned dose based on age group, given as 5 mg tablets or equivalent dose as oral pediatric formulation.

Ruxolitinib (tablet or oral pediatric formulation) should be taken approximately 12 hours apart (morning and night) without regards to food. Ruxolitinib will be administered by Investigator or delegate, or self-administered by the subject or parent/legal guardian in an outpatient setting.

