Subjects should be instructed not to take ruxolitinib at home on the days of the scheduled pre-dose blood collection for PK and biomarker samples. Refer to [Section 8.5.1](#) and [Section 8.5.2](#). Dosing will be administered after pre-dose blood collection at these visits.

If a dose is vomited within any timeframe after dosing, re-dosing should not occur.

If a dose is missed, the subject should not take an additional dose, but should take the prescribed dose at the next scheduled dosing time.

The ruxolitinib dose as assigned on Cycle 1 Day 1 (based on age) must **not** be changed until the subject completes the Cycle 7 Day 1 visit assessments, unless dose adjustments are needed to manage safety events. After Cycle 7 Day 1, the Investigator must re-evaluate the assigned ruxolitinib dose based on the subject's age and/or growth. Dosing based on growth should be adjusted if the newly calculated dose is a > 10% change from the previously calculated dose. Subjects should remain on the same formulation until Cycle 7 Day 1. Any change in formulation prior to Cycle 7 Day 1 requires approval from the Sponsor. All dose changes must be recorded on the Dosage Administration Record electronic case report form (eCRF).

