A new study ICF will need to be signed if the investigator chooses to re-screen a subject after a subject has screen failed. A new subject number will be assigned, the subject will be entered in the IRT as a re-screen and a new re-screen eCRF will be entered. All required screening activities must be performed when the subject is re-screened for participation in the study. An individual subject may only be re-screened once for the study.

Subjects meeting all inclusion and exclusion criteria will be assigned to one of 4 dose groups according to their age.

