The duration of exposure to investigational treatment in patient-years is a total of the duration of exposure to investigational treatment in years from all the patients in the Age group.

Duration of exposure to systemic corticosteroid

Duration of exposure to systemic corticosteroid treatment (days) = (last date of exposure to systemic corticosteroid) – (date of first administration of systemic corticosteroid) + 1.

Duration of exposure to systemic corticosteroid in patient-years

The duration of exposure to systemic corticosteroid in patient-years is a total of the duration of exposure to systemic corticosteroid in years from all the patients in the Age group.

Cumulative dose

The **planned cumulative dose** for ruxolitinib refers to the total planned dose per protocol up to the last dose date.

The **actual cumulative dose of ruxolitinib** refers to the total actual dose of ruxolitinib as documented in the Study Treatment eCRF.

For patients who did not take any drug the cumulative dose is by definition equal to zero.

Dose intensity and relative dose intensity of ruxolitinib

Subjects receive ruxolitinib in doses twice a day (bid). For purposes of reporting dose intensity, a summary over the dose by day (total daily dose) is provided.

Dose intensity (DI) of ruxolitinib for patients with non-zero duration of exposure is defined as follows:

$DI \text{ (mg / day or mg/m}^2\text{/day)} = \text{Actual cumulative dose (mg or mg/m}^2\text{) of ruxolitinib / Duration of exposure to ruxolitinib (days)}$.

In case the study includes subjects who taper off ruxolitinib and later re-start ruxolitinib treatment due to cGvHD recurrence, the duration of exposure excluding “taper off periods” will be used as denominator for dose intensity.

For patients who did not take any drug, the DI is by definition equal to zero.

Planned dose intensity (PDI) is defined as follows:

$PDI \text{ (mg/day or mg/m}^2\text{/day)} = \text{Planned Cumulative dose (mg or mg/m}^2\text{) / Duration of exposure (days)}$.

The PDI of ruxolitinib with daily dose schedule is according to protocol for the three age groups:

- Age group 1: 20 mg/day
- Age group 2: 10 mg/day
- Age group 3: 8 mg/m²/day using the baseline BSA

Relative dose intensity (RDI) is defined as follows:

$RDI = DI \text{ (mg / day or mg/m}^2\text{/day)} / PDI \text{ (mg / day or mg/m}^2\text{/day)}$.

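### For a child who passes a 6th or 12th birthday on treatment the protocol leaves the dose ambiguous, and the SAP's planned dose intensity and adverse-event tables make no allowance for an age-based change

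*Protocol*

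**What the plan says.** Several parts of the protocol tie the dose to an age group that does not change:

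- Section 6.1.1: "Ruxolitinib will be administered orally twice per day at the assigned dose based on age group".
- Section 8.1 treats the age groups as dose groups: "Subjects meeting all inclusion and exclusion criteria will be assigned to one of 4 dose groups according to their age".
- Section 3, repeated in SAP 1.1: "Subjects will remain in the age group throughout the study based on the age at the time of start of treatment".
- Tables 6-4 and 6-5 give reduction and re-escalation levels by group. The Group 2 row starts at 5 mg BID, and its re-escalation ends there.

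Section 6.1.1 also contains a rule that depends on age over time: "After Cycle 7 Day 1, the Investigator must re-evaluate the assigned ruxolitinib dose based on the subject's age and/or growth". A threshold follows, but for growth only: "Dosing based on growth should be adjusted if the newly calculated dose is a > 10% change from the previously calculated dose". No threshold or procedure is given for age.

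Section 6.5.1 then sets a ceiling: "Based on the subject's age, the ruxolitinib dose will not exceed the starting dose level defined for that age Group".

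SAP 2.4.1 fixes the planned dose intensity (PDI): "The PDI of ruxolitinib with daily dose schedule is according to protocol for the three age groups", namely 20 mg/day, 10 mg/day, and 8 mg/m²/day at baseline body surface area (BSA). The same section reports treatment summaries by dose within age group if more than one dose is assigned in a group. SAP 2.8 presents all safety tables by age group.

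**The concern.** The doses on either side of the 12th birthday differ: Section 4.2 gives "5 mg BID for 6-12 years; and 10 mg BID for 12-18 years". If the group fixed in Section 3 also fixes the dose, a Group 2 child who turns 12 stays at 5 mg BID. If re-evaluation for age means what it appears to mean, the same child can move to 10 mg BID. Nothing says which applies, so two sites could dose the same child differently and both cite the protocol.

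Toxicity management is affected too. Section 6.5.1 allows no departure from mandatory reductions, and Table 6-3 orders them as steps of one dose level. For a child who entered in Group 2 and was re-dosed at 12, the documents do not say which row of Table 6-4 to use, and the Group 2 row has no 10 mg BID level from which to step down.

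In the analysis, by-age-group safety tables are naturally read as safety at that group's dose. Relative dose intensity (RDI) is read as adherence to the planned dose. Both readings fail if the planned dose changed with age and the outputs do not show it.

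**Working it through.** **1. The plan's own figures.** PDI is twice the BID dose: 2 × 10 = 20 mg/day (Group 1), 2 × 5 = 10 mg/day (Group 2), 2 × 4 = 8 mg/m²/day (Group 3). All three SAP values reproduce.

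**2. The two readings side by side.**

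| | Dose stays with entry group | Dose follows current age |
|---|---|---|
| Section 3; dose by group in 6.1.1 and 8.1 | Met as written | Must be limited to analysis grouping, which is not stated |
| Age re-evaluation in 6.1.1 | No effect: Group 2 has a flat dose, and in Group 3 only growth acts | Has effect |
| Cap in 6.5.1 | Entry group's dose | Current group's dose |
| Tables 6-4 and 6-5 | Entry row | Row not stated |
| SAP PDI | Consistent, growth adjustment in Group 3 apart | Wrong after a birthday |

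Under either reading some passage needs correction.

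**3. Difference in dose.**
- Turning 12 in Group 2: 10 / 5 = 2-fold.
- Turning 6 in Group 3: 4 mg/m² against a flat 5 mg, both BID. BSA is not given, so 0.65 to 0.9 m² is assumed. Then 4 × 0.65 = 2.6 mg and 4 × 0.9 = 3.6 mg, with ratios 5 / 2.6 = 1.92 and 5 / 3.6 = 1.39. The doses agree only at 5 / 4 = 1.25 m².

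**4. Effect on RDI for a Group 2 child moved to 10 mg BID.**
- After the change: 20 / 10 = 2.0.
- Over 39 cycles (39 × 28 = 1092 days), if changed at Cycle 7 Day 1 (after 6 × 28 = 168 days) with no reductions: (168 × 10 + 924 × 20) / (1092 × 10) = 20160 / 10920 = 1.85.

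**5. Children who could cross a boundary.** Amendment 2 reports 22, 17 and 7 enrolled in Groups 1 to 3, which make up the total of 46, so Group 4 is empty. Assume entry ages uniform within group (widths 6 and 4 years) and y years on drug. The expected number crossing is 17 × y/6 + 7 × y/4.

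| Years on drug | Group 2 | Group 3 | Total of 24 |
|---|---|---|---|
| 1 | 2.8 | 1.8 | 4.6 (19%) |
| 2 | 5.7 | 3.5 | 9.2 (38%) |
| 3 | 8.5 | 5.25 | 13.8 (57%) |

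**6. Share of exposure after a birthday, at the three-year maximum.** Children who cross spend on average 1.5 of 3 years beyond the boundary. That is 0.50 × 1.5/3 = 25% of Group 2 exposure and 0.75 × 1.5/3 = 37.5% of Group 3 exposure. The share at a changed dose would be somewhat lower, since no such change is allowed before Cycle 7 Day 1.

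**The case against.** A consistent reading exists. The cap in 6.5.1 opens with the subject's age, and the Amendment 1 log describes it as clarifying the maximum dose by age. The cap may therefore move with the child, with Section 3 governing grouping for analysis only. Section 6.5.1 also begins with children who do not tolerate the schedule, so the cap may limit only re-escalation after toxicity. The footnote to Table 6-5 calls the escalations outside Group 1 examples. All of this stands as a possible reading. A reader might therefore go too far in inferring that the cap forbids a Group 2 child from ever receiving the Group 1 dose; 6.5.1 does not say that. But the documents do not state the consistent reading either. It leaves the dose-group wording in 6.1.1 and 8.1 unexplained, the row of Table 6-4 unspecified and the SAP's PDI wrong.

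The SAP also handles part of this. A reader might infer that exposure is reported only by entry group and hides any change. SAP 2.4.1 does not support that: it splits treatment summaries by dose within age group where more than one dose is assigned, and it lists doses with reasons for change. That rule does not extend to the adverse-event tables or to the fixed PDI.

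Finally, the 57% in the table might be taken as the expected share affected. It is an upper figure that needs every child to take drug for three years. Sections 6.1.5 and 6.1.5.2 provide for stopping for lack of benefit and for tapering in responders from Cycle 7 Day 1.

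**Conclusion.** The point holds as an ambiguity with consequences for reporting; it does not show that any child was dosed wrongly. For a child passing a 6th or 12th birthday, the text supports two doses: 2-fold apart at 12, and about 1.4- to 1.9-fold apart at 6 under the assumed BSA range. The number who could be affected is about 4.6, 9.2 or at most 13.8 of 24 for one, two or three years on drug, given uniform entry ages.

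A reader might infer that the primary result is at risk. The documents do not support that. Section 6.1.1 bars dose changes before the Cycle 7 Day 1 assessments except for safety, and SAP 2.5.4 includes a breach of that rule among the deviations excluded in the sensitivity analysis. The effect falls on later dosing, on RDI, and on longer-term safety by age group, which SAP 2.2.1 repeats for the final report. The change should be made because it is cheap and those groups hold only 17 and 7 children. Which dose rule is right is for the sponsor to decide; no view is taken here.

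**What to change.** **Protocol.** Reconcile Sections 3, 6.1.1 and 6.5.1 with Tables 6-4 and 6-5. State whether the group fixed at entry is for analysis only, and which group's cap and table rows apply after a birthday.

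**SAP 2.4.1.** Calculate PDI from the protocol dose in force at each time, in place of one value per entry group with baseline BSA. The SAP already defines planned cumulative dose as the dose planned per protocol up to the last dose, so this follows its own general definition. It also covers growth adjustments in Group 3.

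**SAP 2.8.** In the adverse-event outputs, flag children whose dose changed for age and events that started after the change, within the entry age group. With such small groups, a flag in tables and listings is enough.

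**Cost.** A protocol clarification, a time-varying planned dose and one dataset flag. Section 6.1.1 already requires every dose change to be recorded. Enrolment was complete by 17-Sept-2021 and treatment lasts at most three years, so by the final SAP of 07-Oct-2024 little dosing can remain. The SAP changes are now the more useful part.
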